4.5.3.2. Simplicity Questionnaire (SIM-Q) Single Medication status version

The Simplicity of Diabetes Treatment Questionnaire (SIM-Q) single medication status version is a brief 10-item measure developed to assess the simplicity and complexity of treatment for T2D. This measure asks participants to think about a specific medication (prior basal insulin or current study treatment) when completing each item on a 5-point scale ranging from "Very complex" to "Very simple." In Study BDCU, only the last 2 questions of the SIM-Q will be completed – "How simple or complex is your medication treatment for diabetes?" and "Overall, how simple or complex is it to manage your diabetes, including medication, checking your blood glucose levels, diet, and any other aspects of diabetes treatment?"

The frequency and proportion of the response for each question will be summarized for each scheduled visit. Treatment comparison will be conducted by Wilcoxon rank sum test.

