Diabetes counseling, SMBG, hypoglycemia training/education		x	X																	Includes diabetes counseling, SMBG, hypoglycemia (see Sections 5.3, 8.3.3). After V3, review as needed
Participant Diary (Electro	onic) a	nd BC	G Met	er																
Dispense e-diary, glucometer, complete training		X																		
Dispense ancillary supplies as needed		X	Х	Х	Х		Х				Х		Х				Х		X	

			]	For p	roced	lures	at the	Scre	ening	/Lead	l In P	eriod l	[ (V1-V	/2) and	d Tre	atmen	t Perio	d II (V.	3-V22)	)
			it Visi	it 23 t	to Vis	it 37,	ЕТ, Ι									Period	l, plea	se see S	ection	1.3.2 Comments
Study Period I – Screenir	1g/Lea	d-In		•	•		•		Study	/ Peri	od II	- Trea	tment	Period	1					comments
Visit Number	1	2	3	4	5	6	7	8	9	10	11	12 13 14	15	16	17	18 19	20	21	22	
Weeks from Randomization	-3	-2	0	1	2	3	4	5	6	7	8	9 10 11	12	14	16	18 20	22	24	26	
Visit Interval Tolerance (days)		±3		±3	±3	±3	±3	±3	±3	±3	±3	±3	±3	±3	±3	±3	±3	±3	+3	
Fasting or Telehealth Visit			F			Т	F	Т	a	Т		Т	F	Т		Т		Т	F	T = telehealth visit; F = fasting visit; a see notes below
Diary compliance check			X	X	X	X	X	X	X	X	X	Х	Х	Х	X	Х	Х	Х	Х	Review FBG, hypoglycemia events, insulin dose
Patient-Reported Outcom	es (Pa	per)																		
Treatment-Related Impact Measure - Diabetes (TRIM-D)			Х																Х	
Patient-Reported Outcom	nes (Ele	ectron	ic)																	
Diabetes Treatment Satisfaction Questionnaire – Status (DTSQs)			X																	
Diabetes Treatment Satisfaction Questionnaire-Change (DTSQc)																			Х	
EQ-5D-5L			Х																Х	
Simplicity Questionnaire (SIM-Q) – Daily Basal Insulin			Х																	

			]	For p	roced	ures	at the	Scre	ening	/Lead	In P	eriod l	[ (V1-V	/2) and	l Tre	atment	t Perio	d II (V	3-V22)	
For	proced	ures a	t Visi	it 23 t	to Vis	it 37,	ET, I	U V, 8	01 an	d 802	(Stuc	ly Peri	iod III	) Safet	y F/u	Period	l, plea	se see S	ection	
Study Period I – Screenin	ng/Lea	d-In							Study	Peri	od II	- Trea	tment	Period	l					Comments
Visit Number	1	2	3	4	5	6	7	8	9	10	11	12 13 14	15	16	17	18 19	20	21	22	
Weeks from Randomization	-3	-2	0	1	2	3	4	5	6	7	8	9 10 11	12	14	16	18 20	22	24	26	
Visit Interval Tolerance (days)		±3		±3	±3	±3	±3	±3	±3	±3	±3	±3	±3	±3	±3	±3	±3	±3	+3	
Fasting or Telehealth Visit			F			Т	F	Т	a	Т		Т	F	Т		Т		Т	F	T = telehealth visit; F = fasting visit; a see notes below
Simplicity Questionnaire (SIM-Q) study intervention																			Х	
Basal Insulin Experience: Preference																			Х	

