Patient-Reported Outcomes	(Elect	ronic)		-	-	-						-		-		-	
Diabetes Treatment Satisfaction Questionnaire - Change						Х						Х					
EQ-5D-5L						Х						Х	Х				
Simplicity Questionnaire – Study Drug (SIM-Q)													Х				Administered only if ET occurs before Visit 26
Basal Insulin Experience: Preference												Х	Х				
Basal Insulin Experience: Likelihood of Incorporating into Routine												Х	Х				
Laboratory Tests and Samp	le Coll	ection	s														
Hematology						Х						Х	Х			Х	
Hemoglobin A1c (HbA1c)		Х				Х		Х				Х	Х			Х	

	For n	roced						`				•		d (801-8), please		ion 1.3.	1
								 						, preude s	Stu Perio	udy od III ty F/u	Comments
Visit Number	23 24	25	26 27	28	29	30	31	32	33 34	35	36	37	ET	UV	801	802	
Weeks from Randomization	28 32	36	40 44	48	50	52	60	64	68 72	74	76	78			80	83	
Visit Interval Tolerance (days)	±7	±7	±7	±3	±7	±3	±7	±7	±7	±3	±7	±3			+7	±7	
Fasting or Telehealth Visit	Т	F	Т	a	Т	F	Т	F	Т	a	Т	F	F		Т	F	T = telehealth visit; F = fasting visit; a see below notes
Clinical chemistry						Х						Х	Х			Х	
Glucose		Х						Х									
Lipid panel						Х						Х	Х			Х	
Urinalysis												Х	Х			Х	
Urine pregnancy													Х			Х	Additional pregnancy testing may be performed as necessary or if required by local regulations
C-Peptide												Х	Х				
eGFR (CKD-EPI)						Х						Х	Х			Х	
UACR						Х						Х	Х			Х	
Pharmacokinetic (PK) samples						Х						Х	Х			Х	All randomized participants

			F	for Tr	eatm	ent Po	eriod (	(V23-V	/37), I	ET, UV	, and	Safety I	F/u Perio	d (801-8	02)		
	For p	roced	ures at	Scree	ning	Perio	d I (V	1-V2)	and T	reatm	ent Pe	riod II (	V3-V22 )	, please	see Sect	ion 1.3.	1
					Stu	ıdy Po	eriod	II - Tr	-	nt Per	iod				Perio	ıdy od III ty F/u	Comments
Visit Number	23 24	25	26 27	28	29	30	31	32	33 34	35	36	37	ET	UV	801	802	
Weeks from Randomization	28 32	36	40 44	48	50	52	60	64	68 72	74	76	78			80	83	
Visit Interval Tolerance (days)	±7	±7	±7	±3	±7	±3	±7	±7	±7	±3	±7	±3	_		+7	±7	
Fasting or Telehealth Visit	Т	F	Т	a	Т	F	Т	F	Т	a	Т	F	F		Т	F	T = telehealth visit; F = fasting visit; a see below notes
Immunogenicity (ADA) samples						Х						Х	Х			Х	All randomized participants.
Stored Samples																	
Exploratory biomarker samples												Х	Х				
Randomization and Dosing																	
Insulin dose assessment /adjustment/documentation	Х	Х	Х	Х	Х	Х	Х	Х	Х	Х	X	Х	Х	Х			See Section 6.5.

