1.1. Objectives, Endpoints, and Estimands

Objectives	Endpoints			
• To evaluate treatment impact between LY3209590 and insulin degludec based on patient- reported outcomes questionnaires	 Change from baseline in TRIM-D at Weeks 26, 52, and 78 DTSQ change (DTSQc) from baseline at Weeks 26, 52, and 78 			
Tertiary				
To investigate the treatment impact of LY3209590 compared with insulin degludec on other measures of efficacy, safety, and patient-reported outcomes	 Efficacy: Percentage of participants achieving HbA1c < 7% at Weeks 26, 52, and 78 Percentage of participants achieving HbA1c < 7% at Week 26 without nocturnal hypoglycemia during treatment phase up to Week 26 Percentage of participants achieving HbA1c ≤ 6.5% at Weeks 26, 52, and 78 Change from baseline in fasting serum glucose at Weeks 26, 52, and 78 Safety: Incidence and rate of Level 2 hypoglycemia events during treatment period Incidence and rate of Level 3 hypoglycemia events during treatment period Incidence of positive treatment-emergent antibody of LY3209590 PK/PD: LY3209590 PK and concentration-response relationships to key safety and efficacy measures Potential intrinsic and extrinsic factors Patient-Reported Outcomes: Change from baseline in SIM-Q at Week 26 Frequency of responses to "Basal Insulin Experience: Likelihood of incorporating into routine" at Weeks 26 and 78 Frequency of responses to "Basal Insulin Experience: Preference" at Weeks 26 and 78 Change from baseline in EQ-5D-5L at Weeks 26, 52 and 			
	• Change from baseline in EQ-5D-5L at weeks 26, 52 and 78			

Abbreviations: CGM = continuous glucose monitoring; DTSQc = Diabetes Treatment Satisfaction Questionnaire – Change Version; HbA1c = hemoglobin A1c; SIM-Q = Simplicity Questionnaire; SMBG = self-monitoring of blood glucose; T2D = type 2 diabetes; TRIM-D = Treatment-Related Impact Measure – Diabetes.

Primary Estimand (for primary objective)

US registration

The *primary* clinical question of interest is: What is the treatment difference between LY3209590 and insulin degludec in change from baseline to Week 26 (Visit 22) in HbA1c in study eligible participants with type 2 diabetes (T2D) currently on basal insulin regardless of treatment discontinuation for any reason and regardless of initiation of rescue medication?

The *treatment regimen estimand* will be used for the primary objective and the attributes are described in the following table.

Treatment Regimen Estimand Attribute	Description		

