	treatment regimen estimand.	observations at these endpoint visits.
		- For efficacy estimand all
		scheduled visits after the day of first dose
		up to Week 78 (Visit 37) in EAS2 for
		MMRM.
Participant-reported	The baseline period is the screening/lead-	• Treatment period starts on the first day
hypoglycemia	in period prior to the first day of study	of study treatment and ends on Week 78
	treatment.	(Visit 37), if study completed treatment
		or on the last dose date of study
		treatment $+$ 10 days and $+1$ day for
		LY3209590 and Insulin Degludec,
		respectively, if discontinued study
		treatment early.
		• Post-treatment period starts from end of
		Treatment period $+1$ day and ends on the
		last day in the study

Analysis	Baseline Observations	Post-Baseline Observations
TEAEs	The baseline period includes the	Safety analysis period starts after the first
	screening/lead-in period up to the first	dose(AE Start Relative to Exposure
	dose of study treatment (AE Start Relative	Assessment in CRF is used to determine)
	to Exposure Assessment in CRF is used to	and ends at the last visit in the study
	determine).	including safety follow-up period.
		Note: An AE will be TEAE if reported to
		be worsen in severity from baseline.
Safety laboratory	The baseline will be the last non-missing	All scheduled visits after the first day of
tests, vital signs and	assessment prior to or on the first day of	study treatment up to follow-up Visit 802
body weight	study treatment.	for MMRM and/or ANCOVA.
	Planned measurements at scheduled visits	Planned measurements at scheduled visits
	will be included.	will be included.
Elevated or low:	Starts from the screening visit and ends	Starts after the day of study treatment and
Laboratory values,	prior to or on the first day of study	ends at the last visit in the study including
vital signs, and body	treatment.	both treatment period and follow-up
weight categorical		period.
measures	All available scheduled and unscheduled	
	measurements will be included. The	All available scheduled and unscheduled
	baseline for weight will be the last non-	measurements in the specified analysis
	missing value during the baseline period.	period will be included.
Anti-LY3209590	Refer to PSAP.	Refer to PSAP.
antibody		
Patient-reported	The baseline will be the data collected at	• All scheduled visits after Week 0
outcomes	Week 0 (Visit 3).	(Visit 3).
		• Last collection after Week 0 (Visit 3).

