4.5.3. Tertiary Patient Reported Outcomes

4.5.3.1. EQ-5D-5L

The EQ-5D-5L (EuroQol Research Foundation 2019) is a standardized 5-item self-administered instrument for use as a measure of health outcome. It provides a simple descriptive profile and a single index value for health status that can be used in the clinical and economic evaluation of health care as well as population health surveys. The EQ-5D-5L assesses 5 dimensions of health:

- mobility,
- selfcare,
- usual activities,
- pain/discomfort, and
- anxiety/depression.

The 5L version, scores each dimension at 5 levels:

- no problems,
- slight problems,
- moderate problems,
- severe problems, and
- unable to perform/extreme problems.

In addition to the health profile, a single health state index value can be derived based on a formula that attaches weights to each of the levels in each dimension. This index value ranges between less than 0 (where 0 is a health state equivalent to death; negative values are valued as worse than dead) to 1 (perfect health).

The second part of the questionnaire consists of EQ Visual Analog Scale (VAS) which records the respondent's self-rated health status. The participant rates his/her perceived health from 0 (the worst imaginable health) to 100 (the best imaginable health). In conjunction with the health state data, it provides a composite picture of the respondent's health status.

The frequency and proportion of each level for a given item will be summarized by study treatment for each scheduled visit. The EQ-5D-5L index, EQ VAS score and their change from baseline will be analyzed by the MMRM model similar to the other efficacy endpoints (see Section 4.4.2.1) for the scheduled postbaseline visits and by the ANCOVA model similar to the TRIM-D for the last non-missing postbaseline observations.

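### SAP 4.5.3.2 specifies no change-from-baseline or baseline-adjusted comparison for SIM-Q, although the tertiary endpoint is change from baseline at Week 26

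*SAP*

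**What the plan says.** **Endpoint.** The tertiary patient-reported outcomes in Protocol 3 and SAP 1.1 include "Change from baseline in SIM-Q at Week 26".

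**Collection.** The schedule in Protocol 1.3.1 has two SIM-Q rows. One, "Simplicity Questionnaire (SIM-Q) – Daily Basal Insulin", is marked at Visit 3 (Week 0). The other, "Simplicity Questionnaire (SIM-Q) study intervention", is marked at Visit 22 (Week 26). Protocol 1.3.2 adds an early termination collection with the comment "Administered only if ET occurs before Visit 26". Only the last two questions of the instrument are used, each on a 5-point scale (Protocol 8.1.5.6.5, SAP 4.5.3.2).

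**Baseline.** For patient-reported outcomes, SAP 4.1 states "The baseline will be the data collected at" Week 0 (Visit 3). For post-baseline data it lists both all scheduled visits and the last collection after Week 0.

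**Analysis.** SAP 4.5.3.2 has two analysis sentences: "The frequency and proportion of the response for each question will be summarized for each scheduled visit", and then "Treatment comparison will be conducted by Wilcoxon rank sum test". Protocol 9.3.4 leaves tertiary analyses to the SAP, so there is no other source.

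**The concern.** The endpoint is a change and the data to form it are collected, but the analysis section does not say how baseline enters the comparison. The analyst would have to choose the ranked variable (Week 26 response or change), the visit, and the place of early termination responses. In an open-label trial with a self-reported outcome, those choices are better fixed in advance. If the Week 26 responses are simply ranked, a status comparison would be reported under a change-from-baseline label, and the precision available from the Visit 3 response would be lost.

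**Working it through.** **1. Compare with the other questionnaires in the SAP.**

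- EQ-5D-5L (4.5.3.1): "The EQ-5D-5L index, EQ VAS score and their change from baseline will be analyzed by the MMRM model". Change is named, and the model has a baseline covariate.
- TRIM-D (4.4.2.3.1): scores and change from baseline go into an MMRM, and the last observation into an ANCOVA with the baseline value.
- DTSQc (4.4.2.3.2): a rank-sum test, but each item of that instrument already asks about change.
- Basal Insulin Experience (4.5.3.3): frequencies and a rank-sum test. Its endpoint in SAP 1.1 is the frequency of responses, so analysis and endpoint agree.
- SIM-Q (4.5.3.2): frequencies and a rank-sum test. The instrument is a status version and its endpoint is a change, so its analysis has the form used for a different kind of endpoint.

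No other SAP text fills the gap. The rule in SAP 4.1 about actual and change values is a descriptive rule for continuous measures. SAP 4.9 declares no departures.

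**2. Size.** The plan states no effect size, SD, correlation or power for SIM-Q, so there is no figure to reproduce. For context, the planned Week 26 completers follow from 939 randomized 2:1 with 15% dropout: 939 × 2/3 × 0.85 = 532.1 and 939 × 1/3 × 0.85 = 266.05, which match the stated 532 and 266.

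Assume equal SDs at baseline and Week 26, and let r be the correlation between them. In large samples, the variance of the treatment difference relative to the unadjusted Week 26 response is:

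- unadjusted Week 26 response: 1
- simple change score: 2(1 − r)
- Week 26 response adjusted for baseline: 1 − r²

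The unadjusted standard error is √(1/532 + 1/266) = 0.075 SD. The powers below assume a true difference of 0.2 SD and two-sided 0.05. Both r and the difference are illustrative.

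| r | Variance, change | Variance, adjusted | Power, unadjusted | Power, change | Power, adjusted |
|---|---|---|---|---|---|
| 0.2 | 1.60 | 0.96 | 0.76 | 0.56 | 0.78 |
| 0.3 | 1.40 | 0.91 | 0.76 | 0.61 | 0.80 |
| 0.4 | 1.20 | 0.84 | 0.76 | 0.68 | 0.83 |
| 0.5 | 1.00 | 0.75 | 0.76 | 0.76 | 0.87 |
| 0.6 | 0.80 | 0.64 | 0.76 | 0.85 | 0.92 |
| 0.8 | 0.40 | 0.36 | 0.76 | 0.99 | 0.99 |

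For r of 0.3 to 0.5, adjustment removes r² = 0.09 to 0.25 of the variance. A change score beats the unadjusted response only when 2(1 − r) < 1, that is r > 0.5. For r from 0 to 1 it never beats adjustment, since 1 − r² = (1 − r)(1 + r) ≤ 2(1 − r).

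**3. Does adjustment answer a change question?** In a linear model that includes the baseline, the treatment coefficient is the same whether the outcome is the Week 26 score or the change. An ordinal model with the baseline response as covariate is the natural counterpart for a 5-point item.

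**The case against.** A reader might go further in three ways that the documents do not support.

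- *The stated endpoint is never tested because raw responses are compared.* SAP 4.5.3.2 does not name the ranked variable. Read with SAP 1.1 and the Week 0 baseline in SAP 4.1, a rank-sum test on change is not excluded. Ranking the responses is the more natural reading, but what can be said is that no test of change is specified.
- *The baseline is collected and then ignored.* SIM-Q has two scheduled visits, Week 0 and Week 26, so a summary at each scheduled visit includes the baseline.
- *Baseline imbalance distorts the Week 26 result.* With randomization, the Week 26 difference and the difference in mean change have the same expectation. Chance imbalance is part of the sampling error that the test already allows for.

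It can also be argued that a rank-sum test is reasonable for single ordinal items, that the endpoint is minor, and that rewording it as the response at Week 26 would also remove the mismatch. All of that is fair. Rewording would settle consistency, but it would leave the precision unused. The baseline asks about the previous basal insulin and Week 26 about the study insulin, so the correlation may be modest and the gain small. None of this supplies the missing specification.

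**Conclusion.** The point holds as a gap between endpoint and analysis: SAP 4.5.3.2 has no change-from-baseline or baseline-adjusted analysis for an endpoint defined as change from baseline. The cost is unclear pre-specification and some lost precision. The unadjusted comparison is not biased.

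The 9% to 25% variance reduction rests on an assumed correlation of 0.3 to 0.5, and on formulas for means applied as an approximation to ranks of 5-point items. It belongs to baseline adjustment only. Over that range a simple change score has relative variance 1.4 to 1.0, no better than the unadjusted response, so it is not recommended for precision. The importance is low: the endpoint is tertiary, lies outside the graphical procedure in SAP 2.1, and supports no confirmatory claim.

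**What to change.** In SAP 4.5.3.2:

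- State that, for each of the two items, the Week 26 response is compared between arms with adjustment for the Visit 3 response and the randomization strata, for example by a proportional-odds model or rank ANCOVA.
- Name Week 26 (Visit 22) as the visit tested.
- State whether early termination responses enter the comparison. The schedule comment refers to Visit 26, which is Week 40, so such a response could fall after Week 26.
- Keep the frequency tables as description.

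The cost is a few sentences in the SAP. Both measurements are already scheduled, and sample size and alpha do not change.

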4.5.3.3. Basal Insulin Experience

Likelihood of incorporating into routine

This is a Lilly-developed, participant-completed question to understand the participant's likelihood of incorporating their study insulin into their diabetes management routine. The question is rated on a 5-point scale with responses ranging from "very unlikely" to "very likely."

The frequency and proportion of the responses will be summarized by study treatment and using Wilcoxon rank sum test for treatment comparison.

Preference

This is a Lilly-developed, participant-completed question to understand the participant's preference for their pre-study or current study treatment. The question is rated on a 5-point scale with responses ranging from "strongly prefer the study insulin" to "strongly prefer my previous insulin." The question also includes a "not applicable" option for participants that stayed on the same insulin in the treatment phase.

The frequency and proportion of the responses will be summarized by study treatment and using Wilcoxon rank sum test for treatment comparison.

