# 4. Study Design

### 4.1. **Overall Design**

Study BDCU is a Phase 3, multicenter, randomized, open-label, comparator-controlled study to evaluate the efficacy and safety of once-weekly basal insulin (LY3209590) compared to insulin degludec in participants with T2D treated with basal insulin.

The study includes a 3-week screening/lead-in period, a 78-week treatment period, and a 5-week safety follow-up period.

Participants will continue prior stable diabetes therapy with 0 to 3 allowed non-insulin antihyperglycemic medications during the study.

Participants will discontinue their previous basal insulin doses at randomization and will be assigned to either LY3209590 or insulin degludec U100. The initial dose for the study treatment will be determined as described in Section 6.1.

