## Type of Participant and Disease Characteristics

- 2. Have a diagnosis of T2D according to the WHO criteria currently treated with basal insulin
- 3. Are receiving  $\geq 10$  units of basal insulin per day and  $\leq 110$  units/day at screening
- 4. Have HbA1c value 6.5%-10% inclusive, as determined by central laboratory at screening
- 5. Have been treated with a stable regimen in the opinion of the investigator of one of the following insulin regimens (includes biosimilars) used according to local product label with or without non-insulin diabetes therapy for at least 90 days prior to screening:
  - once-daily U100 or U200 insulin degludec
  - once-daily U100 or U300 insulin glargine
  - once or twice-daily U100 insulin detemir (Levemir [Novo Nordisk A/S., Bagsvaerd, Denmark]), or
  - once or twice-daily human insulin NPH.

Acceptable non-insulin diabetes therapies may include 0 to up to 3 of the following:

- dipeptidyl peptidase (DPP-4) IV inhibitors
- SGLT2 inhibitors
- metformin
- alpha-glucosidase inhibitors, or
- GLP-1 receptor agonists.

**Note:** All non-insulin diabetes therapies must be used in accordance with the corresponding local product label at the time of screening, and participants should be willing to continue stable dosing throughout the study according to the protocol.

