## **Prior/Concurrent Clinical Study Experience**

- 18. Are currently enrolled in any other clinical study involving an IP or any other type of medical research, judged not to be scientifically or medically compatible with this study
- 19. Have participated, within the last 30 days in a clinical trial involving an IP. If the previous IP has a long half-life, 3 months or 5 half-lives (whichever is longer) should have passed prior to Visit 1 (Week -3)
- 20. Have previously completed or withdrawn from this study after having signed the ICF or any other study investigating LY3209590 after receiving at least 1 dose of the study basal insulin
- 21. Are investigator site personnel directly affiliated with this study and/or their immediate families. Immediate family is defined as a spouse, parent, child, or sibling, whether biological or legally adopted
- 22. Are Eli Lilly and Company employees or are employees of any third party involved in the study who require exclusion of their employees.

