# 6.3. Measures to Minimize Bias: Randomization and Blinding

This is an open-label study. Investigators and participants will be unblinded to the assigned treatment groups. Assignment to treatment groups will be determined by an IWRS. Participants will be randomly assigned to 1 of the 2 treatment groups in 2:1 ratio (LY3209590:insulin degludec) at Visit 3 (Week 0). Stratification will be by country, HbA1c stratum at Visit 1 (Week -3) (<8.0%,  $\geq$ 8.0%), and the type of basal insulin regimen at randomization (a. typical once-daily basal insulin; b. U-300 or NPH BID regimens which need reduction in total daily dose (TDD)/conversion to equivalent dose for typical once-daily U-100 basal insulin regimen).

All study IP will be assigned by IWRS. Site personnel will confirm that they have located and are dispensing the correct IP by entering a confirmation number found on the IP label into the IWRS.

The Lilly study team members who are closely involved in data interpretation and analysis planning will remain blinded throughout the course of the trial; only a minimum number of Lilly personnel will see the randomization table and treatment assignments before the study is complete. The investigator should make every effort to preserve the blinding when contacting the Lilly study team members, including the Lilly clinical research physician or scientist.

Interim analyses will be conducted under the auspices of an external DMC. Only the external statisticians from the SAC will have access to the unblinded data that are presented to the DMC. The SAC and members of the DMC will abide by the principles and responsibilities described in the DMC charter, which include all unblinded information confidential until the planned unblinding of the trial.

An early PK/PD unblinded transfer may also be conducted. Only a small group of personnel can be unblinded to the data for the potential PK/PD analysis and must keep information confidential until the planned unblinding of the trial.

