4.4.2.1.3. Analysis of Fasting Blood Glucose

The analysis of fasting blood glucose (FBG), measured by SMBG, will be analyzed (in both CN and SI units). If a subject does not indicate which BG measurement was fasting, the FBG value will be assigned programmatically by designating the FBG as the first measurement between 5am-10am. These programmatically derived FBG values will also be included in the analysis.

4.4.2.2. **Other Safety Endpoints**

The safety measures based on CGM data will be analyzed as described in Section 4.4.2.1.1. For other safety measures, the details are provided in Section 4.6.

4.4.2.3. **Patient Reported Outcome**

The analyses for patient-reported outcomes will be based on the EAS2 data.

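### The Preference item is compared by a Wilcoxon test with no rule for 'not applicable', an answer that properly arises in the degludec arm only; ranking the remaining answers would compare groups that are no longer as randomized

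*SAP*

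**What the plan says.** Preference is a tertiary patient-reported endpoint at Weeks 26 and 78 (Protocol Section 3, SAP 1.1). Protocol 8.1.5.6.7 and SAP 4.5.3.3 describe one participant-completed question on a 5-point scale, from strong preference for the study insulin to strong preference for the previous one. A further answer, 'not applicable', is an "option for participants that stayed on the same insulin in the treatment phase".

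The planned analysis in SAP 4.5.3.3 is: "The frequency and proportion of the responses will be summarized by study treatment and using Wilcoxon rank sum test for treatment comparison". Neither document says how 'not applicable' enters that test, and neither limits the comparison to participants whose insulin changed.

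Four other statements decide who can give the answer and what the analysis can adjust for:

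- Eligible prestudy regimens include "once-daily U100 or U200 insulin degludec" (Protocol 5.1, criterion 5). LY3209590 is not among them.
- Participants "will be assigned to either LY3209590 or insulin degludec U100" (Protocol 4.1).
- Exclusion criterion 20 rules out people who took part in "any other study investigating LY3209590 after receiving at least 1 dose of the study basal insulin" (Protocol 5.2).
- Randomization is stratified by "the type of basal insulin regimen at randomization (a. typical once-daily basal insulin; b. U-300 or NPH BID regimens" (Protocol 6.3), so degludec is not a stratum of its own.

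On the data used, SAP 4.4.2.3 states: "The analyses for patient-reported outcomes will be based on the EAS2 data".

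**The concern.** 'Not applicable' has no position between the two ends of the scale. A rank test on the five ordered answers therefore leaves it out, unless a rule assigns it a score, and no rule is written. SAP Version 2 adopted the Wilcoxon test in place of a chi-square test because the responses are ordinal (SAP Table 1), but this one answer is not ordinal.

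Leaving it out affects the arms unequally. A prestudy degludec user assigned to degludec has stayed on the same insulin and may answer 'not applicable'. The same kind of participant assigned to LY3209590 has changed insulin and rates a preference. Whether a participant is in the test then depends jointly on prestudy insulin and assigned arm. Ordinary missing-data reasoning does not repair this, and the rank sum test has no covariate for prestudy insulin.

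At stake is the meaning of one p-value. The question asks for a comparison with the previous insulin. If former degludec users judge LY3209590 differently from former glargine, detemir or NPH users, the arms can differ on this item with no treatment difference among everyone else.

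**Working it through.** **Step 1. Who can properly answer 'not applicable'.**

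| Prestudy basal insulin | Assigned LY3209590 | Assigned degludec U100 |
|---|---|---|
| Degludec (U100 or U200) | changed insulin, rates preference | stayed on degludec, 'not applicable' |
| Glargine, detemir, NPH | changed insulin, rates preference | changed insulin, rates preference |

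Only one of the four cells leaves the ranked data.

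**Step 2. Denominators.** The documents give no sample size, power or effect for this item. I use the planned Week 26 completers (Protocol 9.5, SAP Section 5), which reproduce: 626 × 0.85 = 532.1 and 313 × 0.85 = 266.05, against the stated 532 and 266.

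**Step 3. Size of the shift.** Let s be the share of prestudy degludec users (not given; assumed 10, 25 and 40%). Suppose there is no arm difference among all other participants, so their Mann-Whitney probability is 0.5. Suppose former degludec users on LY3209590 have probability 0.5 + d against the ranked degludec arm (d assumed). If 'not applicable' is left out, the overall probability is

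(1 − s) × 0.5 + s × (0.5 + d) = 0.5 + d·s.

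With n1 = 532 and n2 = 266(1 − s), and ties ignored, SE = √[(n1 + n2 + 1)/(12·n1·n2)]. The two-sided 5% test rejects with probability P(|Z + d·s/SE| > 1.96).

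| s | 'Not applicable' in degludec arm | Counterparts kept in LY3209590 arm | n2 | SE | Reject, d = 0 | d = 0.05 | d = 0.10 |
|---|---|---|---|---|---|---|---|
| 10% | 27 | 53 | 239 | 0.0225 | 5% | 5.6% | 7.3% |
| 25% | 67 | 133 | 200 | 0.0240 | 5% | 8.2% | 18.1% |
| 40% | 106 | 213 | 160 | 0.0260 | 5% | 12.0% | 33.6% |

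For example, at s = 25% and d = 0.10 the shift is 0.025, and 0.025/0.0240 is 1.04 standard errors.

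**Step 4. Check by simulation.** A tie-corrected Wilcoxon test was run on a five-category item, with 20,000 runs per setting. The assumed response distribution was 10, 15, 25, 25 and 25%, identical in both arms outside prestudy degludec users. Former degludec users on LY3209590 differed by an assumed odds ratio.

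| Share | OR 1 | OR 1.5 | OR 2 | OR 3 |
|---|---|---|---|---|
| 10% | 5.1% | 5.9% | 7.8% | 11.7% |
| 20% | 5.3% | 8.5% | 15.8% | 31.2% |
| 30% | 4.7% | 12.5% | 27.1% | 55.5% |
| 40% | 5.2% | 17.0% | 40.1% | 76.3% |

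With prestudy degludec users left out of both arms, rejection stayed between 4.7% and 5.3% in every setting.

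**The case against.** A reader might infer more from the SAP than it says. Four points are fair.

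- **The SAP does not state that the answers are dropped.** SAP Section 1 leaves table specifications to separate documents, where a rule may exist. This stands: the consequence is conditional on testing ranked answers only. That is nonetheless what the stated test does on this scale by default. Scoring 'not applicable', for instance at the midpoint, would enter a non-preference as data in one arm.
- **The proportions need not have different denominators.** 'Not applicable' is one of the offered answers and can be shown as a sixth row over all respondents. The problem reaches the proportions only if that row is left out.
- **It does not follow that the degludec arm is rated only against other insulins.** The answer is a participant's choice, and no baseline rule enforces it. Whether a move from U200 to U100 degludec counts as the same insulin is undefined, so some former U200 users may rate a preference. This would dilute the imbalance by an unknown amount.
- **The rejection rates are not a forecast.** Share and departure are assumed, and zero departure gives no inflation. The denominators are planned Week 26 completers. EAS2 also cuts data at rescue, and nothing was computed for Week 78.

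One could also keep everyone and show preference by prestudy insulin, since former degludec users on LY3209590 are the only participants sure to have used both study insulins. That serves description well, but it does not give the two-arm test a randomized basis.

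**Conclusion.** The concern holds in conditional form. SAP 4.5.3.3 pairs a rank test with an answer that cannot be ranked and that properly occurs in one arm only, and it states no rule. Run on ranked answers, the test compares all LY3209590 respondents with a degludec arm from which prestudy degludec users have been removed, wholly or in part. That the comparison is then not as randomized follows from the documents. That it misleads requires preference to vary by prestudy insulin, which they neither support nor exclude.

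The illustrated false-positive rate runs from the nominal 5% to about 34% by formula, and higher under the more extreme simulated inputs. All of it rests on assumed shares and departures. The weight is low: a tertiary item in an open-label trial, outside the multiplicity procedure (SAP 2.1), with no bearing on primary or key secondary conclusions.

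**What to change.** In SAP 4.5.3.3, Preference:

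- Make the treatment comparison, in both arms, only among participants whose prestudy basal insulin was not degludec (U100 or U200). Prior treatments are recorded at Visit 1 and prestudy insulin type is already a baseline summary variable (SAP Appendix 1), so the restriction precedes randomization. It also removes the U200-to-U100 ambiguity from the test.
- Treat any 'not applicable' answer left in that set as missing.
- Report 'not applicable' counts by arm, and the ratings of prestudy degludec users, descriptively.

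The cost is a few SAP sentences and a smaller comparison. At an assumed 25% share, about 399 versus 200 remain (532 × 0.75 and 266 × 0.75). The degludec figure is the same as if 'not applicable' were simply left out, so the added loss is about 133 LY3209590 participants. The SE then rises from 0.0240 to √[(399 + 200 + 1)/(12 × 399 × 200)] = 0.0250.
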